11.e Every chemotherapy cycle (day 1, or up to 3 working days before)

1. Clinical evaluation (doctor/nurse), to include NCI toxicity scores from previous cycle (see Appendix XI) and current WHO PS (see Appendix VII)
2. Check FBC, U&Es, and LFTs (see regimen details in Appendix I for critical values).
3. Measure and record magnesium levels.
4. Recalculate drug doses if patients' weight has changed by more than 10%, or follow local policy.
5. Record Cetuximab administration details for patients in Arm B.
6. These data should be collated on the **Treatment Form** which is returned to UoSCTU every 6 weeks (i.e. after every 3 cycles of OxMdG or IrMdG)

Patients should also complete QoL questionnaires during both pre- and post-operative chemotherapy at the beginning of cycle 4 with OxMdG and IrMdG.

11.f Surgery

Surgical data will be recorded on the surgery form and returned to UoSCTU within four weeks of the date of surgery. Investigators should make local arrangements to ensure that facilities to snap-freeze samples are available during surgery (if possible). Pathology samples (normal and tumour tissue) obtained following liver resection surgery should be requested and sent to the Cancer Sciences Tissue Bank, Southampton (see section 11c) for those patients who have given consent.

11.g After the end of treatment

After completion of study treatment patients will be followed up with the following tests and procedures every 3 months for 2 years, and every 6 months thereafter until progression for a further 3 years and/or death, using the **Progress report & follow-up form**:

1. Clinical examination.
2. Chest, abdomen and pelvis CT scan (or equivalent imaging). Chest x-ray only to be performed if chest CT not available.
3. A QoL form should also be completed every 3 months for the first year and every 6 months thereafter.
4. Magnesium levels should be measured 6-8 weeks after the last dose of Cetuximab and at intervals until hypomagnesaemia has resolved.
5. Documentation of survival status and further anticancer treatments will be done. All deaths should be reported to UoSCTU using the Death CRF.

Patients who progress whilst in follow-up should come off protocol follow-up but treatment and care outcome data should still be collected. The follow-up only form should be completed at the same study time points.

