- For patients at high risk of steroid side effects (e.g. diabetics) or for those who develop toxicity attributable to steroids (e.g. dyspepsia; dysphoria; etc), the oral steroid should be omitted.

Scheduled tests

- FBC and clinical assessment (NCI toxicity scores) should be performed on the day of starting each cycle (or within 3 working days before) and the results available before starting.
- Biochemistry (including creatinine, bilirubin, magnesium and either AST or ALT) is done at the same time as FBC.
- If patient is clinically jaundiced bilirubin level must be reviewed prior to administration of Oxaliplatin.
- If patient has symptoms of possible hypomagnesemia, check magnesium level and correct as advised (see Appendix XIII).

Toxicity and dose adjustments for OxMdG plus Cetuximab

Allergic/hypersensitivity reactions - Cetuximab

- Severe grade 3/4 hypersensitivity reactions have occurred in 2.2% of patients treated with Cetuximab. One death from angio-oedema has been reported.

- Signs include rapid onset of airway obstruction, urticaria and/or hypotension. 80% occur during or within one hour of the first infusion, but reactions can occur with later infusions.
- **Cetuximab must be administered under the supervision of a physician experienced in the use of antineoplastic medicinal products. Close monitoring is required during the infusion and for at least 1 hour after the end of the infusion. Availability of resuscitation equipment must be ensured.**
- Treatment depends on the grade or severity of the reaction, as follows:

CTC Grade Allergic/hypersensitivity reaction	Treatment
Grade 1 Transient flushing or rash, drug fever <38°C	Decrease the Cetuximab infusion rate by 50% and monitor closely for any worsening. The total infusion time for Cetuximab should not exceed 240 minutes (4 hours).
Grade 2 Rash; flushing; urticaria; dyspnea; drug fever ≥ 38°C	Stop Cetuximab infusion. Administer bronchodilators, oxygen etc. as medically indicated. Resume infusion at 50% of previous rate once allergic/hypersensitivity reaction has resolved or decreased to grade 1 in severity, and monitor closely for any worsening.

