- Dose modifications for grade 3 toxicity are summarised on the algorithm below. For CTC grade 1 or 2: continue treatment with Cetuximab. If a patient experiences grade 3 skin toxicity (rash effects $> 50\%$ of body surface area), Cetuximab therapy may be delayed for up to 14 days without changing the dose level. If grade 3 skin toxicity occurs for a second and third time, Cetuximab therapy may again be delayed for up to 14 days with concomitant dose reductions to 400 mg/m^2 and then 300 mg/m^2 . Cetuximab dose reductions are permanent. Patients must discontinue Cetuximab if more than 2 consecutive infusions are withheld or grade 3 skin toxicity occurs for a fourth time despite appropriate dose reduction. If the toxicity resolves to grade 2 or less by the following treatment period, treatment may be resumed.
- The investigator should also consider concomitant treatment with topical and oral antibiotics. Grade 1 acneiform eruption: consider treatment with topical antibiotics (e.g. Topical Metronidazole or Erythromycin). Systemic antibiotics (e.g. a second generation tetracycline such as Doxycycline 100mg po daily) should be considered for grade 2 acneiform eruption, and are mandatory for grade ≥ 3 reactions. The threshold for referral to the dermatology clinic should be planned locally but all patients with grade ≥ 3 reactions and probably all with grade 2 reactions should be referred for advice and management. If pruritus occurs an oral antihistamine is advised. Dry skin often occurs (and may contribute to pruritus) general advice on replacing soap with oil for washing, avoidance of hot water for baths or showers and use of emollient creams are beneficial; topical corticosteroids can be used according to local practice. Fissures may occur in dry skin and topical dressings (e.g. hydrocolloid dressings and as advised by your dermatologist) are helpful.

- Colloidal oatmeal preparations (Aveeno, Nature's Gate) can be effective if applied at least 3 times daily⁴⁸. These are available at chemists or on the internet.

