Appendix XI – NCI common terminology criteria for adverse events (v3.0)

Toxicity	0	1	2	3	4	5
NAUSEA	None	Loss of appetite without alteration in eating habits	Oral intake decreased without significant weight loss, dehydration or malnutrition; IV fluids indicated < 24hrs	Inadequate oral caloric or fluid intake; IV fluids, tube feedings, or TPN indicated ≥ 24hrs	Life-threatening consequences	Death
VOMITING	None	1 episode in 24 hours	2-5 episodes in 24 hours; IV fluids indicated < 24hrs	≥ 6 episodes in 24 hours; IV fluids, or TPN indicated ≥ 24hrs	Life-threatening consequences	Death
ANOREXIA	None	Loss of appetite without alteration in eating habits	Oral intake altered without significant weight loss or malnutrition; oral nutritional supplements indicated	Associated with significant weight loss or malnutrition; IV fluids, tube feedings or TPN indicated	Life-threatening consequences	Death
ALOPECIA	Normal	Thinning or patchy	Complete	-	-	-
RASH: ACNE/ ACNEIFORM	None	Intervention not indicated	Intervention indicated	Associated with pain, disfigurement, ulceration, or desquamation	-	Death
RASH: HAND-FOOT SKIN REACTION	None	Minimal skin changes or dermatitis (e.g., erythema) without pain	Skin changes (e.g., peeling, blisters, bleeding, oedema) or pain, not interfering with function	Ulcerative dermatitis or skin changes with pain, interfering with function	-	-
NAIL CHANGES	None	Discoloration; ridging (koilonychias); pitting	Partial or complete loss of nail(s); pain in nailbed(s)	Interfering with ADL	-	-
PAIN	None	Mild pain not interfering with function	Moderate pain: pain or analgesics interfering with function, but not interfering with ADL	Severe pain: pain or analgesics severely interfering with ADL	Disabling	-
MUCOSITIS/ STOMATITIS (clinical exam)	None	Erythema of the mucosa	Patchy ulcerations or pseudomembranes	Confluent ulcerations or pseudomembranes; bleeding with minor trauma	Tissue necrosis; significant spontaneous bleeding; life-threatening consequences	Death
MUCOSITIS/ STOMATITIS (functional/ symptomatic)	None	Minimal discomfort, intervention not indicated	Symptomatic, medical intervention indicated but not interfering with ADL	Stool incontinence or other symptoms interfering with ADL	Symptoms associated with life-threatening consequences	Death

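### Both cetuximab regimens describe grade 3 skin toxicity by rash area alone, but Appendix XI grades acneiform rash by severity features and has no area criterion

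*Protocol*

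**What the plan says.** Appendix I of the protocol sets out the cetuximab skin-toxicity rule twice in the same terms, once for OxMdG plus cetuximab and once for IrMdG plus cetuximab. It is stated in CTC grades: "For CTC grade 1 or 2: continue treatment with Cetuximab". The next sentence starts "If a patient experiences grade 3 skin toxicity (rash effects" and completes the parenthesis with an extent of more than 50% of body surface area.

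At a first grade 3 event cetuximab may be delayed for up to 14 days at the same dose. A second and third event add permanent reductions to 400 and then 300 mg/m². At a fourth event cetuximab must stop. Resumption also depends on the grade: "If the toxicity resolves to grade 2 or less by the following treatment period, treatment may be resumed".

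A separate bullet in the same section covers antibiotics and referral. Systemic antibiotics "should be considered for grade 2 acneiform eruption, and are mandatory for grade" 3 and above. All patients with reactions at that level, "and probably all with grade 2 reactions should be referred for advice and management".

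Section 11.e asks for a clinical evaluation at every cycle, "to include NCI toxicity scores from previous cycle (see Appendix XI"). Appendix I repeats the requirement under its scheduled tests: "FBC and clinical assessment (NCI toxicity scores) should be performed on the day of starting each cycle". In Appendix XI the grade 3 entry for acne/acneiform rash reads "Associated with pain, disfigurement, ulceration, or desquamation".

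**The concern.** The parenthesis in the dose rule measures how far the rash extends. The acneiform row of Appendix XI measures how bad it is. An investigator who scores the rash from Appendix XI and then turns to Appendix I for the dose is given one label, grade 3, with two descriptions that need not agree.

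What is at stake is patient safety and consistent dosing of the experimental drug. Appendix I says that the rash is usually on the face, upper chest and back. A painful or ulcerated rash confined to those sites may well cover less than half the body surface, and so fall outside the only description of grade 3 that the dose rule gives.

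**Working it through.** No power or event calculation applies, and the plan gives no figure to reproduce. The check sets the two definitions side by side. The inputs are the parenthesis in the two skin-toxicity sections of Appendix I and the acneiform row of Appendix XI.

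**Step 1. Cross-classify an acneiform rash.** The four features are those in the grade 3 entry of Appendix XI. In the same row, grades 1 and 2 are separated only by whether intervention is indicated.

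| Extent | Any of the four features? | Appendix XI | Appendix I parenthesis | Agree? |
|---|---|---|---|---|
| Half the surface or less | No | Grade 1–2 | Not met | Yes |
| Half the surface or less | Yes | Grade 3 | Not met | **No** |
| More than half | No | Grade 1–2 | Met | **No** |
| More than half | Yes | Grade 3 | Met | Yes |

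The definitions disagree in both directions. The second row is the safety case.

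**Step 2. Look for an area criterion elsewhere in Appendix XI.** The printed hand-foot and nail rows have none either.

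**Step 3. Compare the other cetuximab grades.** Appendix I puts grade 3 hypomagnesaemia below 0.4 mmol/l, and Appendix XI gives below 0.4 down to 0.3 mmol/l. The hypersensitivity grades also match. The skin parenthesis is the exception.

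**Step 4. Size the dose steps for one affected patient.**
- Delay: up to 14 days, which is one fortnightly interval.
- First reduction: 1 − 400/500 = 20%.
- Second reduction: 1 − 300/500 = 40%.
- Fourth occurrence: cetuximab stops.

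**Step 5. Check resumption.** A rash that shrinks below half the surface but stays painful or ulcerated no longer meets the parenthesis. It could be read as grade 2 or less, although Appendix XI still makes it grade 3.

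**Step 6. Try to count patients.** Appendix I cites grade 3 or higher skin reactions in about 12% of patients. Applied to the 134 per arm in section 18, this gives 0.12 × 134 ≈ 16. That figure neither counts nor bounds the discordant cases: it does not say which definition was used, and a rash that one definition misses may lie outside it. The number affected remains unknown.

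**The case against.** Several points on the other side are good.

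- **Scope.** The dose rule speaks of skin toxicity, which is wider than acneiform rash. Appendix XI states that it prints only selected categories. The area criterion may belong to a CTC category that is not reproduced, and a widespread rash without the four features would have no other explicit trigger. This stands. It means that the parenthesis cannot be called a wrong definition, only an incomplete one for the rash that the section is mainly about.
- **Antibiotics and referral.** A reader might infer that a painful rash on a small area would also lose mandatory antibiotics and firm referral. The text does not support that. Those rules sit in a separate bullet without the area parenthesis, speak of acneiform eruption, and can be read directly on the Appendix XI grades.
- **Missing figure.** The dose-modification algorithm is not shown in the text available here and may state the criterion. This lowers confidence.
- **Safeguards.** Section 9.a directs dose changes to Appendices I–IV and doubts to the trials unit. Section 9.b stops cetuximab for unacceptable toxicity, section 13.a allows withdrawal for it, and section 21.b leaves the investigator free to give other treatment. The delay at a first event is optional. Nothing obliges anyone to continue cetuximab through an ulcerated rash.

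These safeguards soften the conflict without resolving it. Referring doubts to the trials unit helps only a reader who notices the mismatch. Appendix I itself labels its scale as CTC, and the acneiform row is among those printed.

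**Conclusion.** The inconsistency is in the text of both cetuximab regimens. Taken literally, an acneiform rash that Appendix XI grades 3, but that covers less than half the body surface, misses the stated trigger for delay, reduction and discontinuation, and could be judged fit for resumption too early. For an affected patient the steps at issue are a delay of up to 14 days, dose cuts of 20% and 40%, and stopping at a fourth event. A first event may be handled the same way under either reading.

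This rests on two assumptions: that Appendix XI is the scale meant by CTC grade in the skin rule, as section 11.e indicates, and that the missing algorithm does not already reconcile the two.

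A reader might go further and infer that the trial's efficacy result is at risk. It is not: the primary PFS comparison is by intention to treat and does not use the rash grade. Severity is minor to moderate and confidence moderate.

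**What to change.** In both skin-toxicity sections of Appendix I, rewrite the parenthesis so that either criterion triggers the rule. For example: *grade 3 skin toxicity (either acneiform rash meeting the grade 3 entry in Appendix XI, with its four features listed here, or any rash covering more than 50% of body surface area)*. Add that cetuximab resumes only when neither criterion is still met. If the algorithm figure states a criterion, bring it into line.

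Do not delete the area criterion, since that would remove the only explicit trigger for a widespread rash without the four features.

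The cost is a wording amendment in two places, with clinical confirmation by the investigators. No extra assessments are needed. The downside is possibly slightly more cetuximab delays or reductions.

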Appendix VIII – Cockcroft & Gault formula	77
Appendix IX – EORTC QLQ questionnaires	78
Appendix X – EQ-5D questionnaire	83
Appendix XI – NCI common terminology criteria for adverse events (v3.0)	85
Appendix XII – Economic evaluation	87
Appendix XIII – Hypomagnesemia	90
Appendix XIV - New EPOC k-RAS Genotype Request Form	92

1. Trial design

2. Summary

Title	
	New EPOC: an open-label randomised trial, comparing OxMdG / IrMdG chemotherapy versus OxMdG / IrMdG chemotherapy plus Cetuximab.
Study population	
	Two hundred and eighty eight colorectal cancer patients with liver metastases deemed resectable in whom the oncologist feels chemotherapy would be beneficial, who are fit for combination chemotherapy, and possess the KRAS-wt genotype confirmed in primary tumour by laboratory analysis.
Study regimen	
	
Patients will be randomised at the start of chemotherapy to receive either:
 
Arm A: OxMdG / IrMdG chemotherapy
 
Arm B: OxMdG / IrMdG chemotherapy with Cetuximab
 
OxMdG: L-folinic acid (175 mg flat dose IV over 2 h) or d,L-folinic acid (350 mg flat dose IV over 2 h), concurrent administration of Oxaliplatin (85 mg/m² IV over 2 h) plus 5 minute bolus of 5FU (400 mg/m²) followed by a 46 h IV infusion of 5FU 2400 mg/m² repeated every 2 weeks as used in the FOCUS trial
 
or
 
IrMdG: Irinotecan 180 mg/m² IV over 30 minutes, L-folinic acid (175 mg flat dose IV over 2 h) or d,L-folinic acid (350 mg flat dose IV over 2 h) plus 5 minute bolus of 5FU (400 mg/m²) followed by a 46 h IV infusion of 5FU 2400 mg/m² repeated every 2 weeks as used in the FOCUS trial in patients intolerant of Oxaliplatin.
 
Cetuximab will be given as a fortnightly dose of 500 mg/m² with OxMdG and IrMdG. Patients will receive 12 weeks of chemotherapy, undergo surgery and then complete a further 12 weeks of chemotherapy.

Study objectives/endpoints	
	The primary endpoint is progression-free survival. Secondary endpoints include pre-operative response rate, overall survival, quality of life and cost effectiveness.
Supplementary studies	
	Patients will be asked for separate consent to use a blood sample and a proportion of their stored pathology samples for translational research projects. These include analyses of EGFR expression, biomarkers of response, DNA repair capacity and other pharmacogenomic studies.

3. Summary of interventions (treatment phase)

	Week ...																																				

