- DPD is the initial and rate-limiting enzyme for 5-FU breakdown. DPD deficiency is an inherited (pharmacogenetic) disorder in which individuals with absent or significantly decreased DPD activity develop life-threatening toxicity following exposure to 5-FU (in either IV or oral form). Reduced drug clearance results in markedly prolonged exposure to 5-FU so that administration of standard doses of 5-FU results in altered 5-FU pharmacokinetics and severe toxicity including mucositis, granulocytopenia, neuropathy

and death. The onset of toxicity usually occurs twice as fast in patients with low DPD activity as compared with patients with a normal DPD activity. Approximately 3-5% of the population has low DPD activity and 0.1% have absent activity. We recommend that (i) patients with a personal or family history suggestive of DPD deficiency should not be enrolled onto New EPOC, and (ii) those who experience grade 3/4 neutropenia and grade 3/4 mucositis after cycle 1 should be considered as potentially having DPD deficiency. If DPD deficiency is suspected, patients should only continue on trial after full recovery but without the further use of a Fluoropyrimidine.

- 5FU may provoke angina attacks or even MI in patients with ischaemic heart disease. Continued treatment with upgraded antianginal medication and reduced 5FU dose may be considered.

Cetuximab plus Oxaliplatin modified de Gramont administration

Patients will receive Cetuximab intravenous infusions at a dose of 500 mg/m² to be administered over 2 hours and thereafter fortnightly infusions. Cetuximab is provided in ready use vials containing 5 mg/ml. Once removed from the vial, Cetuximab must be used within 8 hours if stored at room temperature.

Please note Cetuximab must be administered under the supervision of a physician experienced in the use of antineoplastic medicinal products. Close monitoring is required during the infusion and for at least 1 hour after the end of the infusion. Availability of resuscitation equipment must be ensured. Vital signs should be checked and recorded before, during, and 1 hour after the Cetuximab infusion. There must be at least one hour between completion of the Cetuximab infusion and the start of chemotherapy.

Day 1 of treatment schedule (14 day cycle)

0:00	IV Chlorphenamine 10mg, Paracetamol 1g p.o., Ranitidine 150mg p.o. IV bolus DDexamethasone 8 mg IV bolus GGranisetron 3 mg (or equivalent) Flush line with 0.9% saline

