- Nail toxicities occur in 8% of patients with Cetuximab, characterised by a paronychia inflammation with associated swelling of the lateral skin folds of toes and fingers, especially great toes and thumbs, which may be painful. It may persist for up to three months after cessation of Cetuximab therapy. Dermatological advice should be sought. Use of daily salt baths and local antiseptic / astringent ointments have been found to be helpful. Anti-inflammatory drugs may help to ease the pain.

Hypomagnesaemia - Cetuximab

- Hypomagnesaemia has been reported in up to 65% of patients following Cetuximab therapy. Patients should have magnesium concentration monitored at baseline, prior to each cycle of chemotherapy and for up to 8 weeks after the last dose of chemotherapy, or until magnesium has normalised, whichever is the longer.
- Fatigue, malaise, tremor, ataxia, carpedal spasm, hyperreflexia, confusion, hallucinations, convulsions and arrhythmias may occur.
- Hypomagnesemia should be corrected by intravenous supplementation if grade 3 (<0.4 mmol/l) or symptomatic. If lesser degrees of hypomagnesemia are detected, oral supplementation may be considered (see Appendix XIII for details).
- Dose modifications for grade 3 toxicity are summarised in the algorithm below. For CTC grade 1 or 2: continue treatment with Cetuximab. If a patient experiences grade 3 toxicity, Cetuximab therapy may be delayed for up to 14 days without changing the dose level. If grade 3 toxicity occurs for a second and third time, Cetuximab therapy may again be delayed for up to 14 days with concomitant dose reductions to 400 mg/m² and then 300 mg/m². Cetuximab dose reductions are permanent. Patients must discontinue Cetuximab if more than 2 consecutive infusions are withheld or grade 3 toxicity occurs for a fourth time despite appropriate dose reduction. If the toxicity resolves to grade 2 or less by the following treatment period, treatment may be resumed.

Dose modifications for Cetuximab-related skin toxicity and hypomagnesaemia:

* These refer to the second and third consecutive week of non-resolving grade 3 toxicity.

Haematological

- Myelotoxicity is similar in frequency as with OxMdG alone. Leucopenia has been reported and attributed to Cetuximab in 8% of patients treated with chemotherapy plus Cetuximab.

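### The 14-day limit on delaying cetuximab and the stop rule counted in withheld infusions do not meet on this trial's fortnightly schedule

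*Protocol*

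**What the plan says.** **Schedule.** Section 2 (Summary, study regimen) states: "Cetuximab will be given as a fortnightly dose of 500 mg/m² with OxMdG and IrMdG". Appendix I repeats this in the introduction to both cetuximab regimens, where the first infusion is "to be administered over 2 hours and thereafter fortnightly infusions".

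**Delay limit, in days.** Appendix I, Skin toxicity – Cetuximab, says that at a first grade 3 event "Cetuximab therapy may be delayed for up to 14 days without changing the dose level". At a second and third event, "Cetuximab therapy may again be delayed for up to 14 days with concomitant dose reductions".

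**Stop rule, in infusions.** The same paragraph continues: "Patients must discontinue Cetuximab if more than 2 consecutive infusions are withheld or grade 3 skin toxicity occurs for a fourth time". The hypomagnesaemia paragraph has the matching rule: "Patients must discontinue Cetuximab if more than 2 consecutive infusions are withheld or grade 3 toxicity occurs for a fourth time".

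**Resumption.** "If the toxicity resolves to grade 2 or less by the following treatment period, treatment may be resumed".

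Both paragraphs appear twice, once under OxMdG plus Cetuximab and once under IrMdG plus Cetuximab, so the rule stands in four places. Each place points to an algorithm. Its figure is not reproduced in the text available here, but its footnote is, and it counts successive weeks of unresolved grade 3 toxicity.

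**Time off treatment.** Section 9.b separately limits Arm B patients to three weeks off treatment, whatever the cause, with an exception after surgery. It also refers to Appendix I for cetuximab dose reductions and delays.

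**The concern.** The two limits sit in one paragraph and govern the same decision, but they use different units. A limit in days and a limit in infusions agree only at a particular dosing interval. If the interval in this trial is not that one, there is a period in which a patient has passed the permitted delay but has not met the condition for stopping.

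At stake is whether an Arm B patient stays on the experimental drug, and whether resuming it counts as a protocol deviation. Section 13 asks for all deviations to be reported, so sites and the trials unit need one answer. With two limits, centres may handle the same toxicity differently, and cetuximab exposure in Arm B may then vary with the sentence a centre relies on.

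**Working it through.** This is calendar arithmetic. No power or significance figure is involved.

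**Inputs**
- Dosing interval: 14 days (Section 2; Appendix I).
- Permitted delay: up to 14 days at each of the first three grade 3 events (Appendix I).
- Stop rule: more than 2 consecutive infusions withheld, that is, the third (Appendix I).
- Rash of grade 3 or higher: about 12% (Appendix I, Skin toxicity – Cetuximab).
- Arm B size: 134 with confirmed kRAS wild type (Section 18), or 288 / 2 = 144 in all.

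**Method.** Day 0 is the due date of the first withheld infusion, and later due dates follow at the dosing interval.
- Delay if the next infusion is given on its due date = number withheld × interval.
- Gap since the last infusion = (number withheld + 1) × interval.
- Day on which the third infusion is withheld = 2 × interval.

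**Results**

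| Interval | Withheld | Delay (days) | Gap since last infusion (days) | Within 14-day limit? | Infusion-count stop met? |
|---|---|---|---|---|---|
| 14 days (this trial) | 1 | 14 | 28 | Yes | No |
| 14 days (this trial) | 2 | 28 | 42 | No | No |
| 7 days (for comparison) | 1 | 7 | 14 | Yes | No |
| 7 days (for comparison) | 2 | 14 | 21 | Yes | No |

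The third infusion is withheld on day 2 × 14 = 28 in this trial, and on day 2 × 7 = 14 under weekly dosing.

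**Reading the table**
1. Under weekly dosing the delay limit and the stop trigger both fall on day 14, so the limits meet.
2. Under fortnightly dosing the delay limit is day 14 and the stop trigger is day 28. They are 28 − 14 = 14 days apart.
3. A patient who resumes after day 14 and up to day 28 has exceeded the permitted delay but has had no more than two infusions withheld.
4. Withholding the second infusion, due on day 14, already takes the delay beyond 14 days. The infusion-count stop therefore cannot be reached without first exceeding the delay limit.

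**Example.** Grade 3 rash is present when an infusion is due (day 0), is still grade 3 on day 14, and is grade 2 on day 28. The 14-day limit has been passed. The infusion-count stop has not been met.

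**Section 9.b.** Three weeks is 21 days. If this limit applies to cetuximab alone and runs from the missed due date, one withheld infusion (14 days) is inside it and two (28 days) are outside. If it runs from the last infusion, even one withheld infusion (28 days) is outside. If it concerns all treatment together, it does not bear on cetuximab withheld while chemotherapy continues. The section does not say which is meant.

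**Scale.** 0.12 × 134 = 16.1 and 0.12 × 144 = 17.3, so about 16 to 17 Arm B patients would be expected to have rash of grade 3 or higher. The pre-operative course is 12 / 2 = 6 infusions, so one withheld is 1/6 = 17% of it and two are 2/6 = 33%.

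**The case against.** The strongest reply is that the two sentences do different jobs. The delay sentence is a permission, and the discontinuation sentence is the only mandatory stop. No sentence says that cetuximab ends for good at day 14, so a centre that stopped there could not cite this text as requiring it. That is right, and it narrows the problem. It does not remove it: the permission has an upper bound of 14 days, and that bound must be exceeded before the infusion-count stop can operate.

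The second reply is that the algorithm may deal with toxicity that does not resolve. Its footnote shows that it has entries for that situation, and one possible reading is that persisting toxicity moves the patient to the second and third steps, each with a further delay. This cannot be confirmed here. A reader might infer that the protocol has no rule at all for toxicity unresolved at day 14; without the figure, that is not supported. What stands is that the running text conflicts with itself, and that a footnote in weeks does not match fortnightly infusions.

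The third reply concerns consequences. Section 18 specifies an intention-to-treat comparison, Section 9.e keeps every randomised patient evaluable whatever treatment follows, and Section 21.b lets the investigator depart from protocol treatment in the patient's interest. A reader might infer that the primary comparison is biased. The documents do not show that.

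**Conclusion.** The conflict holds. On fortnightly dosing the two limits are 14 days apart (day 14 and day 28), and resumption between them is outside one and inside the other. This occurs in all four places where the rule is written. It is a conflict between stated rules on staying on the experimental drug, and it matters for safety and for consistent exposure in Arm B.

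Three limits on the conclusion:
- **Timing.** A reader might place the stop at a 42-day delay, the delay that three withheld infusions would produce. The trigger is the withholding of the third infusion, which happens on its due date, day 28.
- **Numbers.** The 16 to 17 patients are all those expected to have rash of grade 3 or higher. Only those still unresolved at 14 days reach the conflict. The protocol gives no figure for them, nor a rate of grade 3 hypomagnesaemia: the quoted figure of up to 65% is for hypomagnesaemia of any grade.
- **Origin.** The limits coincide on a 7-day schedule and the footnote is in weeks, so the wording may have been written for weekly dosing. That is an inference; the protocol does not say so.

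The result assumes that infusions are counted on 14-day due dates and that delay is measured from the first missed due date.

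**What to change.** Reconcile the skin-toxicity and hypomagnesaemia paragraphs under both cetuximab regimens in Appendix I, the algorithm and its footnote, and the three-week limit in Section 9.b. Specifically:
- put the maximum delay and the discontinuation trigger in one unit suited to fortnightly dosing, so that they meet without gap or overlap;
- make the running text and the algorithm agree on what happens when grade 3 toxicity has not resolved at the end of the permitted delay;
- state whether the Section 9.b limit applies when cetuximab alone is withheld, and from which date it runs.

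Which limit applies is for the sponsor's clinical team to decide. The cost is a wording amendment or a clarification letter to centres, with no additional procedures.
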